**Adverse events reported on ABT-888 (Veliparib) trials, but for which there is insufficient evidence to suggest**

that there was a reasonable possibility that ABT-888 (Veliparib) caused the adverse event:

**BLOOD AND LYMPHATIC SYSTEM DISORDERS** - Bone marrow hypocellular; Blood and lymphatic system disorders - Other (pancytopenia)

**CARDIAC DISORDERS** - Cardiac disorders - Other (Takotsubo cardiomyopathy); Heart failure; Left ventricular systolic dysfunction; Palpitations; Sinus bradycardia; Sinus tachycardia

**EAR AND LABYRINTH DISORDERS** - Vertigo

**EYE DISORDERS** - Blurred vision

**GASTROINTESTINAL DISORDERS** - Abdominal distension; Ascites; Colitis; Colonic obstruction; Dental caries; Dry mouth; Duodenal ulcer; Dyspepsia; Dysphagia; Enterocolitis; Esophagitis; Flatulence; Gastritis; Gastroesophageal reflux disease; Lower gastrointestinal hemorrhage; Mucositis oral; Obstruction gastric; Rectal hemorrhage; Rectal pain; Small intestinal obstruction

**GENERAL DISORDERS AND ADMINISTRATION SITE CONDITIONS** - Chills; Edema limbs; Fever; Flu like symptoms; Malaise; Non-cardiac chest pain; Pain

**HEPATOBILIARY DISORDERS** - Hepatic failure; Hepatobiliary disorders - Other (cirrhosis)

**INFECTIONS AND INFESTATIONS** - Appendicitis; Catheter related infection; Infections and infestations - Other (peritonsillar abscess); Lung infection; Lymph gland infection; Mucosal infection; Sepsis; Shingles; Skin infection; Upper respiratory infection; Urinary tract infection

**INJURY, POISONING AND PROCEDURAL COMPLICATIONS** - Bruising; Dermatitis radiation; Radiation recall reaction (dermatologic)

**INVESTIGATIONS** - Alanine aminotransferase increased; Alkaline phosphatase increased; Aspartate aminotransferase increased; Blood bilirubin increased; Cardiac troponin I increased; Creatinine increased; Electrocardiogram QT corrected interval prolonged; Lipase increased

**METABOLISM AND NUTRITION DISORDERS** - Hyperglycemia; Hypernatremia; Hypoalbuminemia; Hypocalcemia; Hypokalemia; Hypomagnesemia; Hyponatremia

**MUSCULOSKELETAL AND CONNECTIVE TISSUE DISORDERS** - Arthralgia; Arthritis; Back pain; Bone pain; Generalized muscle weakness; Muscle cramp; Myalgia; Neck pain; Pain in extremity

**NEOPLASMS BENIGN, MALIGNANT AND UNSPECIFIED (INCL CYSTS AND POLYPS)** - Tumor pain

**NERVOUS SYSTEM DISORDERS** - Ataxia; Cognitive disturbance; Depressed level of consciousness; Dysarthria; Extrapyramidal disorder; Intracranial hemorrhage; Lethargy; Memory impairment; Movements involuntary; Paresthesia; Peripheral motor neuropathy; Peripheral sensory neuropathy; Presyncope; Reversible posterior leukoencephalopathy syndrome; Stroke; Syncope; Tremor

**PSYCHIATRIC DISORDERS** - Agitation; Anxiety; Confusion; Depression; Insomnia; Psychiatric disorders - Other (emotional instability); Psychosis; Restlessness

**RENAL AND URINARY DISORDERS** - Dysuria; Hematuria; Proteinuria

**RESPIRATORY, THORACIC AND MEDIASTINAL DISORDERS** - Cough; Dyspnea; Epistaxis; Hypoxia; Nasal congestion; Pharyngolaryngeal pain; Pleural effusion; Pneumonitis; Respiratory failure

**SKIN AND SUBCUTANEOUS TISSUE DISORDERS** - Alopecia; Dry skin; Hyperhidrosis; Nail changes; Palmar-plantar erythrodysesthesia syndrome; Pruritus; Purpura; Rash acneiform

**VASCULAR DISORDERS** - Flushing; Hot flashes; Hypertension; Hypotension; Vascular disorders - Other (brainstem infarction)

**Note:** ABT-888 (Veliparib) in combination with other agents could cause an exacerbation of any adverse event currently known to be caused by the other agent, or the combination may result in events never previously associated with either agent.

### 7.1.2 Adverse Event List(s) for Topotecan and Carboplatin

Please refer to appropriate package inserts for the comprehensive list of adverse events for each agent.

**Topotecan:** Myelosuppression, fatigue, nausea, vomiting, oral/colonic/perianal mucositis, abdominal pain, anorexia, constipation or diarrhea, alopecia, fever.

**Carboplatin:** Myelosuppression, nausea, vomiting, rash, transaminitis, nephrotoxicity (mainly when given with other potential nephrotoxins), electrolyte wasting, peripheral neuropathy (rare).

## 7.2 Adverse Event Characteristics

- **CTCAE term (AE description) and grade:** The descriptions and grading scales found in the revised NCI Common Terminology Criteria for Adverse Events (CTCAE) version 5.0 will be utilized for AE reporting. All appropriate treatment areas should have access to a copy of the CTCAE version 5.0. A copy of the CTCAE version 5.0 can be downloaded from the CTEP web site [http://ctep.cancer.gov/protocolDevelopment/electronic\\_applications/ctc.htm](http://ctep.cancer.gov/protocolDevelopment/electronic_applications/ctc.htm).
- **For expedited reporting purposes only:**
  - AEs for the agent that are ***bold and italicized*** in the CAEPR (*i.e.*, those listed in the SPEER column, Section 7.1.1) should be reported through CTEP-AERS only if the grade is above the grade provided in the SPEER.
  - Other AEs for the protocol that do not require expedited reporting are outlined in section 7.3.4.
- **Attribution of the AE:**
  - Definite – The AE is *clearly related* to the study treatment.
  - Probable – The AE is *likely related* to the study treatment.
  - Possible – The AE *may be related* to the study treatment.
  - Unlikely – The AE is *doubtfully related* to the study treatment.
  - Unrelated – The AE is *clearly NOT related* to the study treatment.

## 7.3 Expedited Adverse Event Reporting

7.3.1 Expedited AE reporting for this study must use CTEP-AERS (CTEP Adverse Event Reporting System), accessed via the CTEP Web site (<https://eapps-ctep.nci.nih.gov/ctepaers>). The reporting procedures to be followed are presented in the “NCI Guidelines for Investigators: Adverse Event Reporting Requirements for DCTD (CTEP and CIP) and DCP INDs and IDEs” which can be downloaded from the CTEP Web site ([http://ctep.cancer.gov/protocolDevelopment/electronic\\_applications/adverse\\_events.htm](http://ctep.cancer.gov/protocolDevelopment/electronic_applications/adverse_events.htm)). These requirements are briefly outlined in the tables below (Section 7.3.3).

In the rare occurrence when Internet connectivity is lost, a 24-hour notification is to be made to CTEP by telephone at [contact]. Once Internet connectivity is restored, the 24-hour notification phoned in must be entered electronically into CTEP-AERS by the original submitter at the site.

7.3.2 Distribution of Adverse Event Reports

CTEP-AERS is programmed for automatic electronic distribution of reports to the following individuals: Principal Investigator and Adverse Event Coordinator(s) (if

applicable) of the Corresponding Organization or Lead Organization, the local treating physician, and the Reporter and Submitter. CTEP-AERS provides a copy feature for other e-mail recipients.

### 7.3.3 Expedited Reporting Guidelines

Use the NCI protocol number and the protocol-specific patient ID assigned during trial registration on all reports.

**Note: A death on study requires both routine and expedited reporting, regardless of causality. Attribution to treatment or other cause must be provided.**

Death due to progressive disease should be reported as **Grade 5 “Disease Progression”** in the system organ class (SOC) “General disorders and administration site conditions.” Evidence that the death was a manifestation of underlying disease (e.g., radiological changes suggesting tumor growth or progression; clinical deterioration associated with a disease process) should be submitted.

Pregnancy loss is defined in CTCAE as “Death in utero.” Any pregnancy loss should be reported expeditiously, as **Grade 4 “Pregnancy loss”** under the Pregnancy, puerperium and perinatal conditions SOC. A pregnancy loss should NOT be reported as a Grade 5 event under the Pregnancy, puerperium and perinatal conditions SOC, as currently CTEP-AERS recognizes this event as a patient death.

A neonatal death should be reported expeditiously as Grade 4, “Death neonatal” under the General disorders and administration SOC.

**Phase 1 and Early Phase 2 Studies: Expedited Reporting Requirements for Adverse Events that Occur on Studies under an IND/IDE within 30 Days of the Last Administration of the Investigational Agent/Intervention **

**FDA REPORTING REQUIREMENTS FOR SERIOUS ADVERSE EVENTS (21 CFR Part 312)**

**NOTE:** Investigators **MUST** immediately report to the sponsor (NCI) **ANY** Serious Adverse Events, whether or not they are considered related to the investigational agent(s)/intervention (21 CFR 312.64)

An adverse event is considered serious if it results in **ANY** of the following outcomes:

- 1) Death
- 2) A life-threatening adverse event
- 3) An adverse event that results in inpatient hospitalization or prolongation of existing hospitalization for  $\geq$  24 hours
- 4) A persistent or significant incapacity or substantial disruption of the ability to conduct normal life functions
- 5) A congenital anomaly/birth defect.
- 6) Important Medical Events (IME) that may not result in death, be life threatening, or require hospitalization may be considered serious when, based upon medical judgment, they may jeopardize the patient or subject and may require medical or surgical intervention to prevent one of the outcomes listed in this definition. (FDA, 21 CFR 312.32; ICH E2A and ICH E6).

**ALL SERIOUS** adverse events that meet the above criteria **MUST** be immediately reported to the NCI via electronic submission within the timeframes detailed in the table below.

Hospitalization	Grade 1 and Grade 2 Timeframes	Grade 3-5 Timeframes
Resulting in Hospitalization $\geq$ 24 hrs	10 Calendar Days	24-Hour 5 Calendar Days
Not resulting in Hospitalization $\geq$ 24 hrs	Not required	

**NOTE:** Protocol specific exceptions to expedited reporting of serious adverse events are found in the Specific Protocol Exceptions to Expedited Reporting (SPEER) portion of the CAEPR.

**Expedited AE reporting timelines are defined as:**

- "24-Hour; 5 Calendar Days" - The AE must initially be submitted electronically within 24 hours of learning of the AE, followed by a complete expedited report within 5 calendar days of the initial 24-hour report.
- "10 Calendar Days" - A complete expedited report on the AE must be submitted electronically within 10 calendar days of learning of the AE.

Serious adverse events that occur more than 30 days after the last administration of investigational agent/intervention and have an attribution of possible, probable, or definite require reporting as follows:

**Expedited 24-hour notification followed by complete report within 5 calendar days for:**

- All Grade 3, 4, and Grade 5 AEs

**Expedited 10 calendar day reports for:**

- Grade 2 AEs resulting in hospitalization or prolongation of hospitalization

For studies using PET or SPECT IND agents, the AE reporting period is limited to 10 radioactive half-lives, rounded UP to the nearest whole day, after the agent/intervention was last administered. Footnote "1" above applies after this reporting period.

Effective Date: May 5, 2011

#### 7.3.4 Additional Protocol-Specific Expedited Adverse Event Reporting Exclusions

For this protocol only, the AEs/grades listed below do not require expedited reporting via CTEP-AERS. However, they still must be reported through the routine reporting mechanism (Section 7.4):

CTCAE SOC	Adverse Event	Grade	≥24h Hospitalization a
Anemia	Anemia	Any	No
Leukopenia	White blood cell decreased	Any	No
Neutropenia	Neutrophil count decreased	Any	No
Neutropenic fever	Febrile neutropenia with or without hospitalization	Any	No
Infection	Infection with Grade 3 or 4 neutrophils with or without hospitalization	Any	No
Thrombocytopenia	Platelet count decreased	Any	No
Mucositis	Mucositis oral/esophagitis	Any	No

a Indicates that an adverse event required hospitalization for ≥24 hours or prolongation of hospitalization by ≥24 hours of a patient.

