### 7.1.1 CAEPRs for CTEP IND Agent

#### 7.1.1.1 CAEPR for Veliparib

### Comprehensive Adverse Events and Potential Risks list (CAEPR) for ABT-888 (Veliparib, NSC 737664)

The Comprehensive Adverse Events and Potential Risks list (CAEPR) provides a single list of reported and/or potential adverse events (AE) associated with an agent using a uniform presentation of events by body system. In addition to the comprehensive list, a subset, the Specific Protocol Exceptions to Expedited Reporting (SPEER), appears in a separate column and is identified with bold and italicized text. This subset of AEs (SPEER) is a list of events that are protocol specific exceptions to expedited reporting to NCI (except as noted below). Refer to the 'CTEP, NCI Guidelines: Adverse Event Reporting Requirements' [http://ctep.cancer.gov/protocolDevelopment/electronic\\_applications/docs/aeguidelines.pdf](http://ctep.cancer.gov/protocolDevelopment/electronic_applications/docs/aeguidelines.pdf) for further clarification. Frequency is provided based on 2310 patients. Below is the CAEPR for ABT-888 (Veliparib).

**NOTE:** Report AEs on the SPEER **ONLY IF** they exceed the grade noted in parentheses next to the AE in the SPEER. If this CAEPR is part of a combination protocol using multiple investigational agents and has an AE listed on different SPEERs, use the lower of the grades to determine if expedited reporting is required.

Adverse Events with Possible Relationship to ABT-888 (Veliparib) (CTCAE 5.0 Term) [n= 2310]			Specific Protocol Exceptions to Expedited Reporting (SPEER)
Likely (>20%)	Less Likely (<=20%)	Rare but Serious (<3%)	
BLOOD AND LYMPHATIC SYSTEM DISORDERS			
	Anemia		Anemia (Gr 3)
	Febrile neutropenia		Febrile neutropenia (Gr 3)
GASTROINTESTINAL DISORDERS			
	Abdominal pain		
	Constipation		Constipation (Gr 2)
	Diarrhea		Diarrhea (Gr 3)
Nausea			Nausea (Gr 3)
	Vomiting		Vomiting (Gr 3)
GENERAL DISORDERS AND ADMINISTRATION SITE CONDITIONS			
Fatigue			Fatigue (Gr 3)
INVESTIGATIONS			
	Lymphocyte count decreased		Lymphocyte count decreased (Gr 4)
	Neutrophil count decreased		Neutrophil count decreased (Gr 4)
Platelet count decreased			Platelet count decreased (Gr 4)
	Weight loss		Weight loss (Gr 2)
	White blood cell decreased		White blood cell decreased (Gr 4)
METABOLISM AND NUTRITION DISORDERS			
	Anorexia		Anorexia (Gr 2)

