### 13.4 Early Stopping Guidelines

In addition to monitoring for futility, we will stop the trial if there is evidence of excess toxicity. We plan to monitor each treatment arm separately for the occurrence of any of following adverse events:

- 1) Grade 4 or higher generalized infection or
- 2) Grade 4 or higher radiologically diagnosed lower GI mucositis or
- 3) Grade 3 or higher hand and foot syndrome or
- 4) Grade 3 or higher cardiac arrhythmias or
- 5) Treatment-related mortality or
- 6) Duration of neutropenia exceeding 60 days

Toxicity will be monitored after every 5 patients. If the risk of any of the above adverse events convincingly exceeds 30% in Arm A or 20% in Arm B, the study PI will contact CTEP for a safety consultation. The stopping rule for toxicity will hold enrollment if the posterior probability of risk being larger than 30% (Arm A) or 20% (Arm B) exceeds 0.75. The prior for this toxicity monitoring rule for Arm A is a beta (2,4) distribution and for Arm B is a beta (1,4). This means that our prior guesses at the proportion of severe toxicities is 33% for Arm A and 20% for Arm B. There is a 90% probability that these proportions are between 7.6% and 65.7%, and 1.2% and 52.7%, respectively. The operating characteristics of the stopping rule are shown below and

based on 5000 simulations.

Toxicity Stopping Rules

Arm B			Arm A		
N toxicities	N patients	Probability of too much toxicity *	N toxicities	N patients	Probability of too much toxicity *
3	5	0.914	3	5	0.850
4	10	0.870	5	10	0.869
5	15	0.837	6	15	0.772
6	20	0.811	8	20	0.811
			10	25	0.841
			11	30	0.773
			13	35	0.807
			15	40	0.836

\* The probability of too much toxicity is the posterior probability of toxicity being larger than 20% for Arm A and 30% for Arm B

Operating Characteristics of stopping rule, based on 5000 simulations:

Arm B			Arm A		
True Toxicity Rate	Probability of declaring treatment too toxic	Average sample size	True Toxicity Rate	Probability of declaring treatment too toxic	Average sample size
10%	0.030	19.7	20%	0.113	36.8
15%	0.101	19.2	25%	0.253	33.2
20%	0.263	18.1	30%	0.468	28.1
25%	0.457	16.4	35%	0.660	23.1
30%	0.643	14.7	40%	0.842	17.6
35%	0.805	12.7	45%	0.943	13.5

To ensure balanced randomization between the 2 arms with respect to disease classification, we will stratify up-front according to the two disease categories described above.

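### Section 7.3.4 waives expedited reporting of listed events at any grade with no exception for death, while Section 7.3.3 requires every death on study to be expedited

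*Combined protocol and SAP*

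**What the plan says.** Section 7.3.3 sets the general rule for deaths: "A death on study requires both routine and expedited reporting, regardless of causality". For other serious events of Grade 3 to 5 it requires a notice within 24 hours, followed by a full report within 5 calendar days.

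Section 7.3.4 then lists protocol-specific exclusions: "the AEs/grades listed below do not require expedited reporting via CTEP-AERS". The events must still be reported routinely. The rows are anemia, white cell decrease, neutrophil decrease, "Febrile neutropenia with or without hospitalization", "Infection with Grade 3 or 4 neutrophils with or without hospitalization", platelet decrease and "Mucositis oral/esophagitis". Every row has *Any* in the grade column and *No* in the column for hospitalization of at least 24 hours. The footnote extends that column to prolongation of an existing stay. Grade 5 and death are not mentioned.

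Section 13.4 counts six kinds of event towards a toxicity hold in each arm. Among them are "Grade 4 or higher generalized infection" and treatment-related mortality. Toxicity is reviewed after every 5 patients.

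**The concern.** A site with a patient who dies of a neutropenic infection finds two instructions. Section 7.3.3 makes the expedited report mandatory. Section 7.3.4 says that it is not required and writes no exception for death. Neither section refers to the other on this point. Section 7.2 sends sites to 7.3.4 for events that need no expedited report, so a site that relies on the waiver has textual grounds.

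The wording may also reach beyond site judgement. The Rave-CTEP-AERS text in Section 7 says that protocol-specific rules, as well as NCI rules, decide which entered events need an expedited report. If *Any* is programmed as written, the system may not prompt for a fatal listed event. The documents do not show how Grade 5 is programmed.

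At stake is prompt notice of deaths in a trial of intensive chemotherapy, and of some events that drive the toxicity hold.

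**Working it through.** **1. The death rule against the waiver.** Section 7.3.3 itself uses Grade 5 for a fatal event: it has deaths from progression reported at Grade 5 and notes that CTEP-AERS reads a Grade 5 entry as a patient death. *Any* grade in 7.3.4 therefore includes fatal events on its face. For a fatal listed event:

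| Source | Expedited report |
|---|---|
| 7.3.3, death on study | Required, whatever the cause |
| 7.3.4, listed event, *Any* grade | Not required |

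**2. The hospitalization column.** For febrile neutropenia and for infection, the row text covers events whether or not the patient is hospitalized, while the column says *No*. If the column governs, a Grade 3 to 5 event that causes or prolongs a stay keeps its 24-hour report. If the row text governs, it does not. Treatment is inpatient (Section 5.1), so prolongation of a stay is a practical question. Nor does the column settle step 1, because these two rows expressly include hospitalized patients.

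**3. Overlap with the stopping rule (13.4).**

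| Event | Waived by 7.3.4 | Counted in 13.4 |
|---|---|---|
| Grade 4+ generalized infection with Grade 3 or 4 neutrophils | Yes | Yes |
| Treatment-related death from a listed event | Yes, on the wording | Yes |
| Febrile neutropenia alone, non-fatal | Yes | No |
| Oral/esophageal mucositis, non-fatal | Yes | No |
| Grade 4+ lower GI mucositis | No | Yes |

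**4. Possible lag, in patients.** Routine data are due at least every 2 weeks (12.2.1, 12.2.2). Section 13.2 states a total of 3 patients per month, but its components are 1-2 at the lead site plus 3 elsewhere, which sum to 4-5. Patients enrolled = monthly rate × days / 30.44.

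- 14 days at 3 per month: 3 × 14 / 30.44 = 1.4
- 14 days at 5 per month: 5 × 14 / 30.44 = 2.3
- 1 day at 3 per month: 3 × 1 / 30.44 = 0.1

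**5. What one unseen event does to the rule.** With x events in n patients, the posterior is Beta(2+x, 4+n−x) in Arm A, compared with 30%, and Beta(1+x, 4+n−x) in Arm B, compared with 20%. A hold needs a probability above 0.75. All 12 tabled boundary values reproduce to three decimals with these thresholds from the body text of 13.4. The table footnote has the two thresholds the other way round, and the values do not reproduce that way (Arm A at 3/5 would be 0.967, not 0.850).

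Removing one event at a boundary always takes the probability below 0.75:

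- Arm A: 5/10 gives 0.869; 4/10 gives 0.722.
- Arm B: 3/5 gives 0.914; 2/5 gives 0.738.
- The closest case is Arm A at 15/40, 0.836, which becomes 0.746 at 14/40.

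So an event not yet seen at a look can defer a hold to the next look. As an illustration, assume that the newest Arm A patient's outcome is unseen at every interim look (200,000 simulated trials):

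| True Arm A rate | Plan: P(hold), mean N | Reproduced | Newest patient unseen |
|---|---|---|---|
| 30% | 0.468, 28.1 | 0.463, 28.0 | 0.396, 30.9 |
| 40% | 0.842, 17.6 | 0.845, 17.5 | 0.811, 20.7 |

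This overstates the effect, because it hides all six kinds of event and the waiver touches only the two in step 3. If events are entered when learned, there is no loss.

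**The case against.** The strongest reply is that no reader should be misled. Section 7.3.4 says that a report is not required, not that it is forbidden, so a site that expedites every death breaks no rule. The death rule is also explicit and independent of cause. This is fair, but it depends on the site choosing the stricter text. A site that relies on 7.3.4 breaches 7.3.3, and the protocol does not warn it.

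The second reply concerns delay, and most of it stands. Section 7 has adverse events entered in Rave when the investigator learns of them. Section 12.2.2 asks for real-time submission, with two weeks only as the outer limit. Section 12.1 gives the principal investigator and statistician access at all times. Nothing says that the stopping rule is fed by CTEP-AERS. A reader might infer that the waiver does delay sight of stopping events; the documents show only that it could.

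Three other stronger readings do not hold:

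- **A clash with the SPEER grades for non-fatal events.** The SPEER exempts febrile neutropenia and anemia only up to Grade 3. But Section 7.2 presents 7.3.4 as a further layer of exclusions beyond the SPEER, and its title calls them additional. A wider exclusion can sit on top.
- **A mucositis overlap with the stopping rule.** The waived mucositis is oral/esophageal; the stopping event is lower GI.
- **Infection and mucositis as the expected causes of toxic death.** Section 2.4 says that mucositis was dose-limiting, but no section gives causes of toxic death.

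**Conclusion.** The inconsistency is real and narrow. For a fatal event on the 7.3.4 list, Sections 7.3.3 and 7.3.4 give opposite answers on expedited reporting, with no rule of precedence. A reader might take 7.3.4 to prevail because it is limited to this protocol, but the text does not say so. For febrile neutropenia and infection, the hospitalization column also disagrees with the row text.

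The link to patient safety monitoring covers two kinds of stopping event: treatment-related death from a listed event, and Grade 4 or higher generalized infection with Grade 3 or 4 neutrophils. Its size is at most about 1.4 to 2.3 patients enrolled before notice. That assumes the full two-week interval and accrual between the stated 3 per month and the summed 5. With prompt Rave entry it is close to nil. The case for correction rests on the contradictory instruction about deaths, not on a shown loss of stopping-rule performance.

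**What to change.** Reconcile 7.3.4 with 7.3.3 by three edits:

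1. State in 7.3.4 that the exclusions do not apply to Grade 5 events or to any death on study.
2. Make the hospitalization column agree with the row text for febrile neutropenia and infection, so that the column has one meaning throughout the table.
3. Check the protocol-specific Rave/CTEP-AERS rules against the corrected table and change them if they treat a fatal listed event as exempt.

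The cost is a sentence, two table cells, a possible change to the rules and a few more expedited reports. Narrowing *Any* for non-fatal events, or adding a real-time flag for Section 13.4 events, would be a sponsor preference and is not needed to resolve the conflict.
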